Additionally, subjects will receive the CGI-I scale prior to each treatment session to evaluate clinical stability. Additionally, **at baseline and after the final treatment**, patients will undergo pure tone audiometry testing for safety screening. If a change in auditory threshold is discovered, the treating physician will inform the patient and discuss whether or not to continue with treatment. Furthermore, if a change is discovered, the patient's hearing will be tested again periodically until either it returns baseline or the clinician determines that the change is permanent.

Post-treatment Assessments

Immediately following completion of last treatment, patients in the AH+ sample will have 1 tube of blood drawn for BDNF levels. Within 1 week following completion of treatment, patients will have repeat of baseline behavioral and ERP methods. Behavioral assessments will also be repeated at 1- and 3-month follow-up timepoints. Response to treatment will be defined as >15% reduction in AHRS score. **After the completion of the 3 month visit, subjects will be offered the opportunity to do one week of optional, open label active treatment using identical procedures to the blinded treatment. Subjects will be seen once after the week of open treatment for a follow-up visit**

Schedule of Events

Please see attached table.

Comparison Samples

Participants in the AH- and non-clinical control samples will take part in a baseline assessment session only. AH- patients will be assessed via the SCID, AHRS, PANSS/SQLS, MATRICS/TMT, and ERP procedure. Non-clinical control participants will be assessed via the SCID-NP procedure.

Genetics Blood draw:

Only AVH+ subjects will be asked to participate in the genetics blood draw.

tDCS is thought to work in part by stimulation of BDNF (Fritsch B, Reis J, Martinowich K, Schambra HM, Ji Y, Cohen LG, Lu B. Direct current stimulation promotes BDNF-dependent synaptic plasticity: potential implications for motor learning. *Neuron*. 2010;66:198-204. PM#2864780). Furthermore, plasma BDNF is known to correlate with CSF BDNF (Pillai A, Kale A, Joshi S, Naphade N, Raju MS, Nasrallah H, Mahadik SP. Decreased BDNF levels in CSF of drug-naive first-episode psychotic subjects: correlation with plasma BDNF and psychopathology. *Int J Neuropsychopharmacol*. 2010;13:535-9) and so represents an appropriate reflection of potential effects of tDCS on CNS plasticity. We predict that an increase in plasma BDNF may serve as a marker of "adequate" tDCS. D-serine is an endogenous modulator of NMDAR function that is known to modulate dendritic architecture in brain (Balu DT, Coyle JT. Neuronal D-serine regulates dendritic architecture in the somatosensory cortex. *Neurosci Lett*. 2012;517:77-81. PM#3400345). D-serine synthesis is dynamically regulated by compounds (e.g. nitric oxide) that also affect brain plasticity (1. Darra E, Ebner FH, Shoji K, Suzuki H, Mariotto S. Dual cross-talk between nitric oxide and D-serine in astrocytes and neurons in the brain. *Cent Nerv Syst Agents Med Chem*. 2009;9:289-94). Although there is less literature regarding effects of tDCS on D-serine regulation, nevertheless addition of this measurement (which is done by the [name] lab) adds little expense to the study and does not require additional phlebotomy. We postulate that successful tDCS will be accompanied by increased D-serine release and possibly dendritic rearrangement in brain, and will be reflected in peripheral (plasma) D-serine concentrations.

In reviewing the literature, we note that there is also evidence that BDNF gene polymorphisms affect response to tDCS (Antal A, Chaieb L, Moliadze V, Monte-Silva K, Poreisz C, Thirugnanasambandam N, Nitsche MA, Shoukier M, Ludwig H, Paulus W. Brain-derived neurotrophic factor (BDNF) gene polymorphisms shape cortical plasticity in humans. *Brain Stimul*. 2010;3:230-7). It has also been demonstrated that individuals with common polymorphisms of the BDNF gene may show differential response to tDCS enhancement of brain plasticity. Thus, for both facilitatory tDCS (24 subjects, 10 heterozygotes) and inhibitory tDCS (19 subjects, 8 heterozygotes), carriers of the Val66Met allele displayed enhanced plasticity. In the present study, we will perform a secondary analysis to evaluate whether Val66 Met carriers show preferential response to tDCS treatment.

You can upload charts or diagrams if any

Criteria for Early Discontinuation

Criteria for Early Discontinuation

Treatment Termination

Study participation for patients in the AH+ sample will be terminated for subjects with a CGI-I worsening of 2 or greater for two consecutive days, or a CGI-S of 6 or 7 at anytime.

Participants in all samples may choose to terminate their involvement at any time.

Blood and other Biological Samples

Please create or insert a table describing the proposed collection of blood or other biological specimens
Blood samples will be drawn for patients in the AH+ sample only. No blood or biological samples will be collected from participants in the AH- or non-clinical control samples.

12 cc at screening will be drawn for blood work-up (Chem 20, Thyroid function) to determine tDCS treatment safety.

30 cc tube of blood will be collected for D-serine and BDNF assessment and genetics (optional).

Assessment Instruments

Create a table or give a brief description of the instruments that will be used for assessment

SCID: 60 min

SCID-NP: 30 min

AHRS: 20 min

PANSS: 30 min

MATRICES battery (without SC): 1 hr

Tone Matching Test: 20 min

SQLS: 15 min

EEG for ERP procedures: 3 hrs

Wong-Baker Faces Pain Rating Scale 1 minute

CGI-S and CGI-I 5 minutes

Brunoni safety scale 5 minutes

Please attach copies, unless standard instruments are used

Off label and investigational use of drugs/devices

Choose from the following that will be applicable to your study

✓ Device

Off label and investigational use of devices

Device #1

Name of the device

BrainStim SYS

Manufacturer and other information

Brain Vision LLC

Approval Status

IDE is approved

IDE#

CE Reg#MED30003

Who holds the IDE/IDE sponsor?

Other

Enter Name

Brain Vision LLC

Research Related Delay to Treatment

Will research procedures result in a delay to treatment?

No

Treatment to be provided at the end of the study

None. This treatment will be added to standard-of-care treatment for persistent auditory hallucinations which consists of use of antipsychotic medications.

Clinical Treatment Alternatives

Clinical treatment alternatives

Standard-of-care treatment for persistent auditory hallucinations consists of use of antipsychotic medications.

Risks/Discomforts/Inconveniences

Risks that could be encountered during the study period

MRI

There are no known risks to the use of MRI per se. However, three areas of concern are addressed in the next section. The first is the safety risk posed by the attraction of ferromagnetic metal objects by high strength magnetic fields. The second is the discomfort some subjects experience during confinement within the bore of the MRI system. The third is the loud noise made by the gradients during imaging. These risks occur for all clinical MRI exams and are not increased by the proposed research. The images obtained from structural and functional scanning are automatically transferred from the scanner to a workstation that strips potentially identifying data from the image headers, writes the data as image volumes identified by study

number only, and stores the data on our password-protected server in a directory only accessible by the study investigators. All MRI studies follow guidelines set by the FDA with regard to specific absorption ratio (SAR), limits on gradient slew rate (dB/dt), and noise. Having ascertained the absence of implanted metal foreign objects using the aforementioned screening form, subjects and staff remove all other metal objects, including clothing with metal clasps, before entering the magnet room. The magnetic properties of unknown material are tested outside the magnet room with a strong permanent magnet. Participants and staff are also instructed to enter the magnet room slowly and to pause at the entrance to determine if any items on their person may be pulling toward the magnet. Participants wear insert earplugs during scanning to reduce noise levels below FDA limits. General Electric engineers have recently measured the sound levels within our scanners and have determined that it is compliant with FDA guidelines.

Some people have reported sensations during MRI scans, such as "tingling" or "twitching" (or, very rarely, a painful sensation), which are caused by changes in the magnetic field that can stimulate nerves in the body. In our experience, no one has had sensations from the MRI that did not stop when the scanning stopped. An acute risk of burns to the skin is presented by medicinal skin patches, and participants will be asked to remove patches before entering the scanner. Some participants may feel uncomfortable or confined once positioned within the bore of the MRI system and it may cause some subjects to feel anxious.

Evaluation

Patients with schizophrenia may experience some discomfort as a result of questions asked during the psychiatric evaluation, but this should be comparable to their experiences in standard care. For participants recruited for the AH+ sample who receive a blood draw: occasionally, redness or a bruise may develop at the site where blood was drawn. If this occurs, it will usually disappear in a few days. Some people become dizzy and faint when their blood is drawn.

tDCS (AH+ Sample Only)

Since the development of tDCS in the 1960's, hundreds of subjects have participated in studies and received tDCS without any adverse effects. There has been no evidence of neuronal damage induced by tDCS: in two evaluations, Nitsche and colleagues (25, 26) found no elevation of neurone-specific enolase (sensitive marker of neuronal damage). McCreery et al.,(27) demonstrated that current densities below 25mA/cm² do not induce brain tissue damage even by applying high-frequency stimulation over several hours. In our protocol, we stimulate with a maximum current density of 0.057 mA/cm², a thousand fold below this limit. Duration of stimulation is an additional factor contributing to potential tissue damage, which has been detected at a minimum total charge of 216 C/cm² (28). (Total charge=current density x stimulation duration.) This protocol exposes subjects to maximum total charges of 0.022 C/cm², which is far below the established safety threshold. Iyer et al. (29) demonstrated the safety of tDCS applied at 1mA and 2mA for 20 minutes to normal subjects and noted some enhancement of verbal fluency after 2mA of stimulation, but no adverse events. A recent study (30) has demonstrated the safety of 1mA of cathodal tDCS for 20 min in patients with refractory epilepsy. The authors concluded that tDCS does not induce seizures and may have an anti-epileptic effect. Fregni et al, in May 2006 (31), report that patients suffering from central pain secondary to traumatic spinal cord injury safely tolerated tDCS at 2mA for 5 consecutive days, 20 min daily, with significant pain improvement but no significant influence on cognitive performance before and

after treatment.

Some participants reported redness, itching, and mild scabbing of the skin under the electrodes during and after tDCS. Some subjects have reported a sunburn like sensation under the electrodes while current was turned on. This has sometimes persisted for an hour or more after the current was turned off. Mild scabbing has also been observed under an electrode, which resolved after a few days. Both of these events (sunburn like sensation and scabbing) appear to be related to drying out of the sponge electrodes, which we learned from another investigator working with tDCS. Since then we have kept the sponges sufficiently moist, and irritation has been minimal or absent, while scabbing has not recurred.

Some subjects may also experience mild nausea during or after the stimulation. In a study involving one-hundred and two subjects, 2.9% of the participants reported feeling nauseous after receiving tDCS (32).

Reported side effects of tDCS include reddening of the skin under the electrodes (reported in two subjects with recently shaved heads) and itching under the electrode sites while the current was turned on.

Genetics: there are potential dangers in releasing DNA information, such as jeopardy to insurability (risk to ability to obtain insurance), discrimination against employers, landlords and others.

Describe procedures for minimizing risks

tDCS

Routine safety procedures are in place to screen subjects prior to scanning, maintain security of the restricted access areas, and ensure that system security features are in good working order.

To minimize chemical reactions at the electrode-skin interface, non-metallic, conductive rubber electrodes, covered completely with saline-soaked sponges will be used, as recommended by Nitsche and Paulus, 2000 (33).

Electrode sponges will be kept moist in order to avoid skin irritation.

A research physician will be present at all times to monitor patient safety.

Operation of cellular (wireless) devices, telephones, or two-way radios may produce changes in device output, and thus should not be used in close proximity (< 1m).

We do not apply electrodes over broken or irritated skin.

The use of other stimulation electrodes during the treatment period will be avoided.

Lead wires are configured so that they cannot be plugged into power outlets such as wall sockets and line cord receptacles.

MRI

In order to minimize risks and discomforts to participants, we will:

- Screen for metallic devices, implants and other contraindications to scanning by using a screening questionnaire.

- Exclude pregnant subjects and conduct a urine pregnancy test prior to scanning.
- We will also exclude subjects with claustrophobia. We will reduce this potential adverse reaction by discussing the procedure prior to entry into the magnet room, by providing the subject with a mirror through which they can look out into the room, and by communicating with the subject over the intercom. If a subject continues to feel uncomfortable, the imaging procedure is terminated and the subject is removed from the magnet.
- Staff will provide adequate medical, safety monitoring and observation during scanning.
- Our staff will be available to provide support, reduce anxiety, optimize the comfort of the subject and remove the subject from the machine if requested.

Evaluation

Psychiatric evaluations will be performed by a trained clinical rater with patient experience. Blood draws will be performed by a trained phlebotomist.

Genetics: blood samples will be coded. No personal identification will link subjects with the blood sample, and the genetic information will not be made available to anyone (including the subject and their physician). We will apply for a certificate of confidentiality as an additional protection.

Methods to Protect Confidentiality

Describe methods to protect confidentiality

All data (written and electronic) will be coded by number. Personal identifying information will be sorted in an electronically secure database at New York Psychiatric Institute. A master list matching subjects with codes will be kept under lock and key, separate from any research records or the computer database, with access restricted to research staff, to the extent permitted by law. Only staff directly involved in this project will have access to the master list linking subject names to code numbers. In the informed consent form, subjects are told that the information they provide and all findings of testing will be kept strictly confidential, with access limited to the research staff, and possibly state or federal regulatory personnel. Subject data will be kept in a computer, but the subject's name will not appear in this database. The information will only be linked to a code number assigned for the purpose of maintaining privacy. Only members of the research team will have access to the computer.

Will the study be conducted under a certificate of confidentiality?

Yes, we have already received a Certificate of Confidentiality

Direct Benefits to Subjects

Direct Benefits to Subjects

Participants may experience no direct benefits from their involvement in this study. For schizophrenia patients receiving treatment, in one prior study using this procedure, a 30% reduction in hallucination severity was observed along with a significant reduction in Positive and Negative Symptoms.

Compensation and/or Reimbursement

Will compensation or reimbursement for expenses be offered to subjects?

Yes

Please describe and indicate total amount and schedule of payment(s).

Include justification for compensation amounts and indicate if there are bonus payments.

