Experimental Therapeutics/Psychiatry

Within the division/department, what Center or group are you affiliated with, if any?

Silvio O. Conte Center for Schizophrenia Research

Unaffiliated Personnel

List investigators, if any, who will be participating in this protocol but are not affiliated with New York State Psychiatric Institute or Columbia University. Provide: Full Name, Degrees and Affiliation.

[name].

Application for Continuation of Research

Status

Current Status of Study:

All research interventions were completed. Only data analysis is ongoing.

Summary of Experiences to Date

Please provide a summary of scientific progress of the study and the experience of research participants, to date. This requirement is designed to allow for the investigator and the IRB to reassess the study's risks and benefits in terms of developments in the field, changing practice patterns, and new IRB policies and procedures.

Study has been completed. Data analysis continues for an R61-R33 application. A manuscript has been submitted to Biological Psychiatry and will be presented at ACNP 2018.

Funding

Have there been any changes in funding status since the prior approval?

No

Have the principal investigator and other investigators made all required disclosures of financial interest in the study sponsor/product?

Yes

Summary

Have there been any study findings, recent literature, or untoward events occurring here or at other sites in the past year which might affect the analysis of the safety, risks or benefits of study participation?

No

Have there been any serious adverse events (serious and/or unanticipated problems involving risks to subjects or others at this site which occurred in the past year)?

No

Have all study staff with a significant role in the design or implementation of the human subject components of this study received required training in human research subject protections?

No

Is the study covered by a certificate of confidentiality?

Yes

Certificate expiration date (mm/dd/yyyy)

12/31/2021

Overall Progress

Approved sample size

120

Total number of participants enrolled to date

75

Number of participants who have completed the study to date

56

Have there been any significant deviations from the anticipated study recruitment, retention or completion estimates?

No

Comments / additional information

Study enrollment is ended.

Sample Demographics

Specify population

schizophrenia

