Total number of participants enrolled from this population to date

65

Gender, Racial and Ethnic Breakdown

Caucasian: 26

African-American: 36

Hispanic: 9

Asian: 1

Other: 3

Male: 56

Female: 19

Summary of Current Year's Enrollment and Drop-out

Number of participants who signed consent in the past year

0

Did the investigator withdraw participants from the study?

No

Did participants decide to discontinue study involvement?

No

Procedures

To create the protocol summary form, first indicate if this research will include any of the following procedures

- ✓ Psychiatric Assessment
- ✓ Neuropsychological Evaluation
- ✓ Collection of Biological Specimens
- ✓ Use of Placebo or Sham Treatment
- ✓ MRI
- ✓ Use of Investigational Drug or Device

Population

Indicate which of the following populations will be included in this research

- ✓ Adults who may have impaired decision-making ability
- ✓ Medically and Psychiatrically Healthy Subjects
- ✓ Adults
- ✓ Adults over 50
- ✓ Individuals with Psychosis

Research Support/Funding

Will an existing internal account be used to support the project?

No

Is the project externally funded or is external funding planned?

Yes

Select the number of external sources of funding that will be applicable to this study

2

Funding Source #1

Is the PI of the grant/contract the same as the PI of the IRB protocol?

Yes

Select one of the following

The grant/contract is currently funded

Source of Funding

Foundation

Sponsor

Stanley Medical Research Institute (SMRI)

Select one of the following

Multicenter(NYSPI is the lead site)

Business Office

CU

Does the grant/contract involve a subcontract?

No

Funding Source #2

Is the PI of the grant/contract the same as the PI of the IRB protocol?

Yes

Select one of the following

The grant/contract is currently funded

Source of Funding

Federal

Institute/Agency

NIMH

Grant Name

Columbia Conte Center

Grant Number

P50 MH086385

Select one of the following

Multicenter(NYSPI is the lead site)

Business Office

CU

Does the grant/contract involve a subcontract?

No

Study Location

Indicate if the research is/will be conducted at any of the following

✓ NYSPI

This protocol describes research conducted by the PI at other facilities/locations

No

Lay Summary of Proposed Research

Lay Summary of Proposed Research

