The purpose of the present research is to test a potential new treatment for auditory verbal hallucinations in schizophrenia that uses transcranial Direct Current Stimulation (tDCS), a neurostimulation technique that passes an extremely weak electric current through the brain. During the treatment, two electrodes are positioned on the scalp above regions of the brain implicated in abnormal cortical activity associated with auditory verbal hallucinations in schizophrenia (1-3). Due to the directional flow of current, one electrode, termed “cathodal”, inhibits cortical activity, and the other, termed “anodal”, increases cortical activity. These electrodes will be placed such that cathodal stimulation is applied to an area associated with hyperactivity and anodal stimulation to an area associated with hypoactivity. One preliminary study has

revealed that this form of neurostimulation can alleviate auditory verbal hallucination symptoms both immediately following five days of treatment and up to three months after the final treatment(4). The goal of this study is to replicate these effects and explore the mechanisms that may underpin them.

45 patients with persistent auditory verbal hallucinations will be recruited to this study. Each individual will participate in behavioral assessments lasting up to 3 hours each and will then be randomized to receive a series of active vs. sham tDCS treatments. For active treatment, patients will have the inhibitory (cathodal) tDCS electrode placed over left auditory cortex relative to an anodal placed over frontal cortex on the right side. tDCS treatments will take place for 20 min per day for 5 consecutive days. For sham, procedures will be similar except that sham (inactive) tDCS treatment will be used. Assessment batteries will then be repeated following completion of treatment and at 1 and 3 mo following treatment. In addition, patients will be offered the possibility to participate in a concurrent magnetic resonance imaging (MRI) study aimed at evaluating the effects of tDCS on activation of auditory cortex during a auditory discrimination task as well as on other imaging parameters related to resting brain activity and metabolism. Patients who agree to participate in this MRI study will be scanned before and after active or sham tDCS.

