In addition to hallucinating patients, we will recruit up to 20 healthy controls and 20 non-hallucinating patients, who will have similar assessments to the patients, but will not receive tDCS. Overall, we hypothesize that tDCS treatment will lead to reduction in hallucinations, improvement in auditory function, and change in MRI measurements so that patients more closely resemble healthy volunteers and non-hallucinating patients.

Background, Significance and Rationale

Background, Significance and Rationale

The term “hallucination” refers to a sensory experience that is not in accordance with reality. For example, many individuals who suffer from schizophrenia have the experience that people are speaking to them (“auditory verbal hallucinations”) even when this is not, in fact, the case. Moreover, the voices experienced by these individuals often include derogatory content, leading to significant emotional distress. In the worst case, hallucinations may “command” individuals to perform acts that are harmful to themselves or others. In some cases, voices are perceived coming from inside the head, although in others they are experienced as coming from outside. Although hallucinations respond adequately to antipsychotic medications in most patients with schizophrenia, for some patients the hallucinations persist and remain a significant source of distress. The present project is directed toward development of a new treatment for persistent auditory verbal hallucinations in individual with schizophrenia.

One theory regarding the etiology of auditory hallucinations is that they reflect overactivity of the auditory region of brain (auditory cortex), especially left temporo-parietal cortex(1), and hypoactivity in the prefrontal cortex, especially dorsolateral and anterior cingulate regions(2, 5). In individuals with persistent hallucinations, these abnormalities persist despite treatment with antipsychotic medication. Transcranial Direct Current Stimulation (tDCS) is a relatively new technique in which small electrodes are placed over specific regions of the scalp and extremely low currents (1-2 mA) are applied to specific brain regions for up to 20 minutes. Depending upon the direction of current flow, these currents may either increase

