(stimulate) or decrease (inhibit) activity in underlying brain regions. It has been reported that applying inhibitory currents over left auditory regions for 20 min per day over 5 consecutive days leads to significant, long-lasting reductions in auditory hallucinations (6). The present study seeks to replicate this finding and will utilize MRI measures of brain activity and metabolism and behavioral assessments to understand the underlying mechanisms.

Specific Aims and Hypotheses

Specific Aims and Hypotheses

The aim of this study is to evaluate the effects on schizophrenia symptoms of tDCS applied with cathodal (inhibitory) electrode over the left temporo-parietal junction and anodal (excitatory) electrode over the left dorsolateral prefrontal cortex.

Our specific hypotheses are:

1. In comparison to sham, active tDCS treatment will decrease the severity of refractory auditory hallucinations in patients with schizophrenia
2. In comparison to sham, active tDCS treatment will decrease the severity of negative schizophrenia symptoms
3. In comparison to sham, active tDCS treatment will normalize auditory function as reflected in stronger prediction error signals in the auditory cortex during the auditory discrimination task and decreased baseline activity in this region.
4. In comparison to sham, active tDCS treatment will normalize auditory function as reflected in reduced cerebral blood flow in auditory cortex and normalized metabolism.
5. Symptom alleviation following active tDCS treatment will be maintained over the course of 3 months

The two control groups (AVH- and healthy controls) will serve as comparison groups for specific AIM 3 and 4 only.

Description of Subject Population

Sample #1

Specify subject population

Schizophrenia patients with auditory hallucinations

Number of completers required to accomplish study aims

60

Projected number of subjects who will be enrolled to obtain required number of completers

75

Age range of subject population

18-55

Sample #2

Specify subject population

Schizophrenia patients without auditory hallucinations

Number of completers required to accomplish study aims

20

Projected number of subjects who will be enrolled to obtain required number of completers

30

Age range of subject population

18-55

Sample #3

Specify subject population

Non-clinical control participants

Number of completers required to accomplish study aims

20

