Projected number of subjects who will be enrolled to obtain required number of completers

30

Age range of subject population

18-55

Gender, Racial and Ethnic Breakdown

Expected racial breakdown is approximately 50% Caucasian, 16% African-American, 16% Hispanic, 16% Asian, and 2% other. Expected gender ratio is 50% male and 50% female.

Description of subject population

60 patients between the ages of 18 and 55 with a SCID diagnosis of schizophrenia or schizoaffective disorder will be enrolled in the study. All participants will exhibit refractory auditory verbal hallucinations, defined as the persistence of daily hallucinations without remission despite antipsychotic medication at adequate dosage for at least 3 months.

In addition to the primary intervention group, two comparison groups will be studied:

1. A group of patients with minimal or no auditory hallucinations (AH-) (n=20); and
2. A group of non-clinical healthy volunteers (n=20)

These subjects will be tested using a subset of the baseline assessment battery used with AH+ patients, but will not receive tDCS or repeat assessments.

All patients will be receiving antipsychotic medication at the time of study entry. Patients will remain on their present dose of antipsychotic medication throughout the treatment interval.

All participants will receive a physical examination and medical history evaluation in order to rule out disorders that might increase risks associated with tDCS, a urine toxicology screen to rule out illicit drug abuse, and a pregnancy test for women of childbearing capacity. After passing all screening criteria, participants may be removed from the study if they do not comply with study procedures, if there is a

change in their medical status, or if an adverse event has occurred.

Recruitment Procedures

Describe settings where recruitment will occur

Patients with schizophrenia will be recruited through the Lieber Schizophrenia Research Clinic and the community by our staff, all of whom will have undergone CITI and HIPAA training. Healthy controls will be recruited from the community.

How and by whom will subjects be approached and/or recruited?

Patients will be recruited from the Lieber Schizophrenia Research Clinic as follows:

1. Clinical psychiatrists and psychologists of each service will be informed about the study.

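### The SAP adds chlorpromazine equivalents to every analysis because of correlations seen in the data, so the headline test is no longer the pre-specified one; separately, the planned numbers of patients do not agree

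*Protocol*

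**What the plan says.** **Covariates (SAP, Statistical analysis).** The primary endpoint is percent change over the seven AHRS items, analysed by a repeated-measures MANCOVA at one week and one month. Baseline AHRS is named as the only pre-specified covariate. CPZE is then added to every analysis because it correlated with baseline AHRS total (r=0.22, p=0.04) and with PANSS P3 (r=0.30, p=0.005). The SAP also reports that neither baseline AHRS nor CPZE differed significantly between groups. It is dated December 17, 2018. The Protocol's continuation form gives the study status as "All research interventions were completed. Only data analysis is ongoing".

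**Planned numbers (Protocol).**
- Lay Summary: "45 patients with persistent auditory verbal hallucinations will be recruited to this study", and "In addition to hallucinating patients, we will recruit up to 20 healthy controls and 20 non-hallucinating patients".
- Description of Subject Population, Samples #1 to #3: 60 completers from 75 enrolled for hallucinating (AH+) patients, and 20 from 30 for each comparison group. The enrolment row reads "Projected number of subjects who will be enrolled to obtain required number of completers".
- The narrative that follows: "60 patients between the ages of 18 and 55 with a SCID diagnosis of schizophrenia or schizoaffective disorder will be enrolled in the study", with 20 in each comparison group.
- Continuation form, Overall Progress: "Approved sample size" is 120, enrolled to date is 75, and "Number of participants who have completed the study to date" is 56. Sample Demographics gives 65 from the schizophrenia population.

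**The concern.** A covariate is worth adding when it predicts the outcome, and it should be chosen before group-labelled data are seen. The SAP's reason meets neither condition. Both correlations are with symptom scores rather than with percent change. The first is with a score that is already in the model. The SAP does not claim imbalance; it reports none that is significant. The text contains a comparison between groups and postdates the end of the interventions, so it was written with group-labelled data in hand. It does not say that the AHRS-only result will still be reported as primary. There are therefore two candidate headline tests, and only one was fixed in advance.

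The numbers matter for a different reason. A trial is judged against its target, and here a reader can find three AH+ figures. Recruiting 45 patients cannot produce 60 completers at any dropout rate.

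**Working it through.** **1. What the two correlations imply about n.** For a Pearson correlation, t = r·√[(n−2)/(1−r²)] on n−2 degrees of freedom, two-sided.

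| n | p for r=0.22 | p for r=0.30 |
|---|---|---|
| SAP | 0.04 | 0.005 |
| 56 | 0.103 | 0.025 |
| 65 | 0.078 | 0.015 |
| 75 | 0.058 | 0.009 |
| 86 | 0.042 | 0.0050 |

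Allowing for rounding of r and p, the first pair fits n=80–96 and the second n=82–91, so both hold for n=82–91. One-sided tests would fit n=69–71. Neither range contains 75, 65 or 56.

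**2. Strength of the stated reason.** Shared variance is 0.22² = 4.8% with baseline AHRS and 0.30² = 9.0% with PANSS P3. The SAP gives no CPZE correlation with percent change.

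**3. Type I error.** Null trials were simulated with 1:1 arms, one averaged outcome (the group main effect), a CPZE–baseline AHRS correlation of 0.22 and two-sided 0.05. The CPZE–outcome partial correlation is an assumption.

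- Either model used alone: 4.8–5.2%.
- CPZE added only if it correlates with baseline AHRS at p<0.05, which approximates the reason in the SAP: 4.9–5.1% (20,000 trials per cell; n of 56 and 86; partial correlation 0, 0.3 and 0.5).
- Success claimed if either model gives p<0.05 (60,000 trials per cell):

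| Partial correlation | 0 | 0.10 | 0.22 | 0.30 | 0.50 |
|---|---|---|---|---|---|
| n=56 | 5.5% | 5.8% | 6.0% | 6.4% | 7.4% |
| n=86 | 5.4% | 5.6% | 6.2% | 6.3% | 7.1% |

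Repeat runs agreed closely (top values 7.4–7.9% at a partial correlation of 0.50).

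**4. Precision given up by leaving CPZE out.** If the CPZE model has 80% power, its noncentrality is 2.80. Without CPZE it is 2.80·√(1−ρ²).
- ρ=0.22: 2.80 × 0.975 = 2.73, power 78.0%, standard error 1/0.975 = 1.025 times as large.
- ρ=0.30: 2.80 × 0.954 = 2.67, power 76.2%, standard error 1.048 times as large.

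**5. Headcounts.**
- Lay summary: 45+20+20 = 85 recruited.
- Sample table: 75+30+30 = 135 enrolled and 60+20+20 = 100 completers.
- 135−120 = 15 above the approved size.
- The narrative's 60 AH+ with the table's 30 and 30: 60+30+30 = 120, which equals the approved size.

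The last sum means that the narrative's 60 could be the AH+ enrolment behind the approval. It could also be the completer figure under the wrong label, because the two 20s beside it are completer figures. The text cannot settle this, and it gives no power target against which to test 45, 60 or 75.

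**The case against.** The SAP is open about the departure: it says what was pre-specified and what was added. Its stated reason is a baseline correlation, and a choice made on that basis does not inflate type I error. A baseline covariate is also a legitimate adjustment. All of this stands. Disclosure nevertheless does not make the adjusted model the pre-specified one, and the SAP makes no commitment to the AHRS-only result.

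On the headcounts, it is fair to say that enrolment ended at 75 on the form's count, so the excess of 135 over 120 exists only on paper, and that rewording a lay summary changes no analysis. That makes it a secondary consistency point.

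A reader might go further in four ways that the documents do not support.
- *CPZE was added to favour a result.* Nothing shows an outcome-driven choice.
- *The p-values are wrong.* The type of test is not stated and both grants are marked "Multicenter(NYSPI is the lead site"), so the correlations may come from a larger set. Study Location, however, answers No to research by the investigator elsewhere. The analysed set is unexplained, not shown to be in error.
- *The trial missed 60 completers, or met 45, because 56 completed.* The 56 is not split by sample, so it only bounds AH+ completers from above if it covers the whole trial. The implied n of 82–91 casts doubt on that.
- *60 from 75 is the right target.* The match of 60+30+30 to 120 counts against assuming so.

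**Conclusion.** The main point holds: the headline model was changed outside the pre-specified plan, for a reason that does not bear on the endpoint. This is true at any n and with one site or several. The statistical cost is small. Type I error stays near 5% under the reason given, and reaches about 5.4–7.4% only if either model could be the headline. That range rests on assumed partial correlations of 0 to 0.5 and on total n of 56 and 86. What is lost is the reader's ability to rule out selection between models.

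The secondary point also holds. AH+ size appears as 45 recruited, 60 enrolled, and 60 completers from 75. Comparison groups are 20 each or 30 each. Totals are 85 or 135 against 120 approved. The plan is inconsistent, and the documents do not say which figure governs.

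**What to change.** **SAP.** Keep the repeated-measures MANCOVA with baseline AHRS as the only covariate as the primary analysis. Report the CPZE-adjusted model beside it as a sensitivity analysis, labelled as chosen after data were seen. State the n, population and type of test behind the two correlations, and correct the p-values if they do not match. The cost is one more model on existing data, plus the loss of precision shown above if CPZE does predict the outcome.

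**Protocol.** Reconcile the lay summary, sample table and narrative with the approved 120. State one planned AH+ enrolment and one AH+ completer target, do the same for each comparison group, and label every figure as enrolled or completed. Then report the actual number of AH+ completers against that target. This costs wording only.
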